10. PARTICIPANT ASSESSMENTS

Table 10 presents the schedule of treatment and follow up visits. Visits should occur within 2 weeks of the scheduled day. If a participant fails to appear for a visit, the investigator will make every attempt to contact them and determine the reason for the missed visit. A participant will be deemed lost to follow-up only after at least 3 attempts to contact him/her have been made over a 4-week period. For participants who present with significant transportation or other barriers that would prevent them from being followed at the Dana-Farber/Brigham and Women's Cancer Center clinics, they may be followed closer to home at outside institutions by local oncologists, and clinical notes will be requested by the study team.

The primary endpoint (feasibility of receipt of fractions) will be assessed at the completion of all treatment fractions.

Medical history and physical exam, which includes general questions about health, medications being taken, current allergies, and assessment of the development of seizures will be taken at

screening, at each weekly visit during radiation therapy, at 4 ± 2 weeks after completion of radiation, and at subsequent follow-up visits every 1-3 months thereafter per usual clinical practice.

Karnofsky Performance Status (KPS) will be assessed at screening, at each weekly visit during radiation, at 4 ± 2 weeks after completion of radiation, and at subsequent follow-up visits every 2-4 months thereafter per usual clinical practice.

Toxicity review will consist of a history at each visit to monitor for relevant toxicity as described in section 9. Toxicity will be assessed at each weekly visit during radiation therapy, at 4 ± 2 weeks after completion of radiation, and at subsequent follow-up visits every 2-4 months thereafter per usual clinical practice.

Quality of life, as per the MDASI-BT: M. D. Anderson Symptom Inventory – Brain Tumor survey) will be assessed at baseline, at 4 ± 2 weeks after completion of radiation, and at subsequent follow-up visits every 2-4 months thereafter per usual clinical practice. The MDASI-BT is performed as part of an institution-wide effort to collect patient-reported outcomes. This is the usual care pattern for such patients. Patients who have significant transportation limitations may follow-up with their local oncologist and forgo the questionnaire.

Head imaging will be obtained at baseline, at 4 ± 2 weeks after completion of radiation, and at subsequent follow-up visits every 2-4 months thereafter per usual clinical practice. Typically, this will consist with an MRI of the brain with contrast (although CT Head and non-contrast scans will be permitted if participants cannot receive standard MRIs). Head imaging will be used to define response as outline in section 12.7.

Follow-up data from these visits will continue to be collected after active participation in the study concludes. Therefore, participants will be followed per protocol for 6 months after completion of radiation treatment. Additional clinical follow up per standard of care will continue until death or loss to follow up, and relevant outcome data will be collected retrospectively during that time.

The length of follow up for the primary outcome measure (feasibility of receipt of fractions) will be 1 month after treatment completion. The length of follow up for all other endpoints will be until death or loss to follow up. This is because the usual clinical care for patients with brain metastases involves a radiation or neuro-oncology visit, history, and an MRI brain every 2-6 months until death or other loss to follow up.

Table 10. Study Calendar

	Visit 1	Visit 2	Visit 3	Visit 4	Visit 5	Visit 6	Every 2-4 months*
	Screening	Radiation Planning	Radiation Start	Week 1 Visit	Week 2 Visit	4-week follow up*	
Informed Consent	X						
Medical History (including assessment of development of seizures) & Physical Exam	X			X	X	X	X
Neurologic Exam	X			X	X	X	X
Karnofsky Performance Status (KPS)	X			X	X	X	X
CT or MRI	X	X				X	X
MDASI-BT	X					X	X
Toxicity Assessment	X			X	X	X	X
Radiation Planning		X					
Radiation Treatment			X	X	X		

*Patients who have significant transportation limitations may follow-up with their local oncologist and also forgo the MDASI-BT

Abbreviations: MDASI-BT: M. D. Anderson Symptom Inventory – Brain Tumor survey

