1. INTRODUCTION

1.1 Study Disease

Glioblastoma is the most common primary malignant brain tumor in adults, occurring at a rate of 3.66 new cases per 100,000 people per year in the United States (1). The role of adjuvant radiation therapy after surgical resection for glioblastoma was established in the 1970s and 1980s through several historic randomized trials comparing radiotherapy to observation (2–4), chemotherapy (3–5), or combination therapy (3–5). These studies largely showed that post-operative radiotherapy increased the median survival from 3.2-6.0 months to 8.0-12.8 months, establishing radiation therapy as a standard component to treatment for glioblastoma.

Modern treatment for glioblastoma has built upon this backbone of post-operative radiotherapy to include concurrent and adjuvant temozolomide chemotherapy, following a landmark study in 2005 showing the addition of chemotherapy to raise median survival from 12.1 months to 14.6 months (6). Despite optimal combined modality therapy with surgery, radiation, and chemotherapy, survival outcomes remain poor with most patients progressing within 10-15 months and surviving only 14.6-16.2 months from their initial diagnosis (7). The prognosis for patients upon first progression is similarly poor, with most patients only surviving approximately 4 months from progression (8,9).

Re-irradiation is a common treatment component for locally recurrent glioblastoma, often in combination with surgery and/or chemotherapy. Based on a large institutional series of 147 patients with recurrent high grade glioma treated with fractionated stereotactic re-irradiation resulting in a median survival of 11 months with excellent treatment tolerance, a standard regimen for re-irradiation is 35 Gy delivered in 10 fractions over two weeks (10). Based on these data the RTOG is actively testing this regimen in a prospective randomized study with and without concurrent bevacizumab therapy for recurrent glioblastoma (11).

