12. STATISTICAL CONSIDERATIONS

12.1 Study Design/Endpoints

Primary Endpoint

The primary outcome measure is the feasibility of delivering a model-adapted radiation fractionation schedule. Feasibility is defined as successful completion of radiation therapy for at least 13 of 14 patients. Successful completion of radiotherapy is defined as receipt of all scheduled fractions of daily radiotherapy within 24 hours of once daily fractions and within 1 hour of three-times daily fractions.

A sensitivity analysis has been performed on the mathematical model, which revealed no significant effect on tumor kill from the timing of once daily radiotherapy. This analysis did reveal the importance of the timing of three-times daily radiation therapy, for which feasibility was defined as treatment within 1 hour of the scheduled time.

Secondary Endpoints

Secondary outcomes and analytic techniques to assess these outcomes will include:

1. Quality of life, as determined by the MDASI-BT index (Appendix B), ascertained at the time of study enrollment, 4 weeks after completion of reirradiation, and every 2-4 months thereafter. We will conduct a longitudinal / repeated measures analysis to assess quality of life (mean MDASI-BT score for items 1-22 in APPENDIX B between 0-24 weeks)
2. Incidence (exact binomial distribution with 95% confidence intervals)

- and time to the development of Grade 3+ acute or delayed CNS toxicity
3. Incidence and time to development of radiation necrosis (Kaplan-Meier plot, Cox regression)
 4. Incidence and time to the development of seizures (Kaplan-Meier plot, Cox regression)
 5. Performance status (longitudinal regression)
 6. Overall survival, defined as the interval from registration to death from any cause (Kaplan-Meier plot, Cox regression)
 7. Progression-free survival, defined as the interval from registration to progression or death, whichever occurs first (Kaplan-Meier plot, Cox regression)
 8. Local recurrence, defined as the interval from registration to local recurrence (Kaplan-Meier plot)
 9. Incidence and time to salvage craniotomy (Kaplan-Meier plot, Cox regression)
 10. Incidence and time to additional systemic treatments after reirradiation (Kaplan-Meier plot)

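### Patients with travel difficulty may skip the follow-up MDASI-BT with no other way to complete it, and the plan does not say how death enters the MDASI-BT and KPS analyses

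*Combined protocol and SAP*

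**What the plan says.** Section 10 schedules the MDASI-BT at baseline, 4 ± 2 weeks after radiation, and every 2-4 months after that. It then adds that patients with serious transport problems "may follow-up with their local oncologist and forgo the questionnaire". The footnote to Table 10 says that such patients "may follow-up with their local oncologist and also forgo the MDASI-BT". Its asterisk marks the 4-week column and the later follow-up column, so the baseline form is not waived. No alternative way of completing the form is described.

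KPS is treated differently. Section 10 states "Karnofsky Performance Status (KPS) will be assessed at screening, at each weekly visit during radiation", and KPS continues at the same follow-up visits. For patients who cannot attend, "they may be followed closer to home at outside institutions by local oncologists, and clinical notes will be requested by the study team". No waiver applies to KPS.

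Patient-reported outcomes come first among the secondary objectives in Section 2.3. Section 12.1 makes the MDASI-BT secondary endpoint 1: "We will conduct a longitudinal / repeated measures analysis to assess quality of life", using the mean of items 1-22 over 0-24 weeks. KPS is endpoint 5, given only as a longitudinal regression with no time window. Section 12.7 refers back to 12.1 and adds RANO definitions. Sections 12.8 and 12.8.2 deal with evaluability and split quality of life by completion of radiotherapy. None of these sections says how a missing form or a death enters either longitudinal analysis.

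**The concern.** There are two separate problems.

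The first is a data-collection rule. A form that is not completed at its time point cannot be recovered later, and this rule permits the loss for a group unlikely to be a random sample of those alive. Every patient enters with KPS of at least 70 (Section 3.1.5) and begins a course of 10 treatment days, three of them with three fractions. Someone who managed that but cannot return for one follow-up visit may have worsened. The RANO text in Section 12.7 takes the same view: it counts non-return because of death or deterioration as progression. If the skipped forms come from sicker patients, the remaining scores are too favourable.

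The second is an unstated estimand. Many patients may die within the 24-week MDASI-BT window. If the analysis summarises observed values, later means describe survivors. If it fits a likelihood-based mixed model, the fitted mean implicitly carries scores past death. The plan does not say which is meant, for the MDASI-BT or for KPS.

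At stake is how the secondary results are read. An apparently preserved quality of life after a new schedule could partly reflect who was left to answer, and the later efficacy trial foreseen in Section 12.2 could inherit that impression.

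**Working it through.** The plan gives no expected completion rate or attrition figure, so there is none to reproduce for this point. Its only sizing figure concerns the primary endpoint: the one-sided 95% exact upper limit for 1 non-adherent patient of 14 computes to 29.7%, against 30% in Section 12.2. It does not depend on the MDASI-BT or KPS.

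**Deaths within the window**

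Inputs:
- n = 14 (Section 12.2).
- Median survival of 11 months, from the re-irradiation series in Section 1.1.
- Median survival of 4 months, from the statement in Section 1.1 about "most patients only surviving approximately 4 months from progression".
- Assumed: exponential survival, with week 0 as the start of each median.

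Formula: S(t) = 0.5^(t / median), with t in months. Week 24 is 24 × 7 / 30.44 = 5.52 months.

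- 11-month median: S = 0.5^(5.52/11) = 0.706. Alive: 14 × 0.706 = 9.9. Dead: 4.1 (29%).
- 4-month median: S = 0.5^(5.52/4) = 0.384. Alive: 14 × 0.384 = 5.4. Dead: 8.6 (62%).

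Expected number alive of 14:

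| Week | 11-month median | 4-month median |
|---|---|---|
| 6 | 12.8 | 11.0 |
| 14 | 11.4 | 8.0 |
| 24 | 9.9 | 5.4 |

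**Forms left at week 24**

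The documents give no skipping rate. Assume that a share q = 10% to 30% of living patients skip. Forms = number alive × (1 − q).

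- 11-month median: 9.9 × 0.9 = 8.9 down to 9.9 × 0.7 = 6.9.
- 4-month median: 5.4 × 0.9 = 4.8 (unrounded inputs) down to 5.4 × 0.7 = 3.8.

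**Shift in the MDASI-BT mean from the waiver alone**

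Let completers have mean m and skippers m + d, where higher is worse on the 0-10 scale. The mean of all living patients is (1 − q)m + q(m + d) = m + qd. The observed-case mean is m. The observed mean is therefore too favourable by qd.

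- Low end: q = 0.1, d = 1, giving 0.1 points.
- High end: q = 0.3, d = 2, giving 0.6 points.

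Both q and d are assumed. A simulation with other assumed inputs, in which frailty raises the chance of skipping and about 20% skip, gave a smaller shift of 0.05 to 0.10 points in the same direction.

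**The case against.** The strongest case against runs as follows. This is a 14-patient, single-arm feasibility study. Its decision rests on 13 of 14 patients completing radiotherapy, and no stated decision uses the MDASI-BT or KPS. Transport limits may mean distance: Section 10 speaks of barriers in general and of follow-up nearer home. The same section already requires repeated contact attempts after a missed visit. The form is collected through an institution-wide usual-care programme, so remote collection would be a new study procedure. With 14 patients and an assumed SD of 1.5 to 2, the standard error of a mean is about 0.40 to 0.53, so most of the 0.1-0.6 range lies within sampling noise. The 4-month median describes survival after progression generally, not survival of patients selected for re-irradiation.

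Much of this stands. The primary endpoint is untouched, the size of the bias is unknown, and 29% dead may be closer to this population than 62%, although the 11-month series covered high-grade glioma more broadly. What does not fall is the rule itself: it gives up data on the first-listed secondary endpoint without offering a substitute. Contact attempts after a missed visit do not collect a form that has been waived. Imprecision does not excuse an avoidable loss that probably runs in one direction.

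A reader might infer three stronger things that the documents do not support:
- That the waiver also flatters KPS. It names only the MDASI-BT; KPS stays scheduled and outside notes are requested.
- That deaths are ignored. The plan is silent, which is different. Deaths are recorded (the Follow-Up Form in Section 11.1 is due within 2 weeks of death), overall survival is its own endpoint, and Appendix A lists KPS 0 as dead without saying whether the regression uses it.
- That 0.6 points is an estimate of the bias. It is the top of a range built wholly on assumed inputs.

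**Conclusion.** The point holds within limits. For the MDASI-BT, the waiver loses follow-up forms that cannot be recovered, probably more from patients who are declining, so quality of life is likely to look somewhat better than it was. The direction rests on transport difficulty being at least partly a matter of health. The magnitude cannot be fixed from the documents, and the 0.1-0.6 point range is illustrative and applies to an observed-case mean.

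For both the MDASI-BT and KPS, the treatment of death is unstated. Under exponential survival at the two medians in Section 1.1, about 4 to 9 of 14 patients would be dead by week 24, and observed values at that time describe the rest. The 24-week window belongs to the MDASI-BT only; for KPS the week-24 count is simply an illustration.

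This affects the interpretation of secondary endpoints, not the feasibility conclusion. It merits correction because the loss is avoidable at little cost.

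**What to change.** In Section 10 and the Table 10 footnote, replace the waiver with completion of the same form by mail, phone or electronically at the same time points. Record the mode of completion, and the reason whenever a form is missing.

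In Section 12.1 or 12.7, commit to reporting at each visit the number alive and the number completing the MDASI-BT, and label MDASI-BT and KPS means as means among patients alive. That also settles that the KPS value of 0 for death does not enter those means.

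A composite that counts death as worsening is optional. If used, it needs a worsening threshold fixed in advance, and it would be driven substantially by survival, which is already an endpoint.

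The cost is an amendment to the text, a few contacts by existing staff for at most 14 patients, and one descriptive table. The downside is a possible small mode effect between clinic and remote completion, which recording the mode makes visible.

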11. DATA COLLECTION

11.1 Summary of Data Submission

Item	Due
Demographic Form Initial Evaluation Form Pathology Report Head Imaging Report	Within 2 weeks after registration
Treatment Form	Within 2 weeks of the end of radiotherapy
MDASI-BT	Within 2 weeks of each follow up as above
Follow-Up Form	Within 2 weeks of each follow up as above Within 2 weeks of progression/relapse and death

11.2 Summary of Dosimetry Data Submission for Protocol Treatment

Item	Due
Final Dosimetry Information Radiotherapy Form Daily Treatment Record	Within 1 week of RT end

12. STATISTICAL CONSIDERATIONS

12.1 Study Design/Endpoints

Primary Endpoint

The primary outcome measure is the feasibility of delivering a model-adapted radiation fractionation schedule. Feasibility is defined as successful completion of radiation therapy for at least 13 of 14 patients. Successful completion of radiotherapy is defined as receipt of all scheduled fractions of daily radiotherapy within 24 hours of once daily fractions and within 1 hour of three-times daily fractions.

A sensitivity analysis has been performed on the mathematical model, which revealed no significant effect on tumor kill from the timing of once daily radiotherapy. This analysis did reveal the importance of the timing of three-times daily radiation therapy, for which feasibility was defined as treatment within 1 hour of the scheduled time.

Secondary Endpoints

Secondary outcomes and analytic techniques to assess these outcomes will include:

1. Quality of life, as determined by the MDASI-BT index (Appendix B), ascertained at the time of study enrollment, 4 weeks after completion of reirradiation, and every 2-4 months thereafter. We will conduct a longitudinal / repeated measures analysis to assess quality of life (mean MDASI-BT score for items 1-22 in APPENDIX B between 0-24 weeks)
2. Incidence (exact binomial distribution with 95% confidence intervals)

- and time to the development of Grade 3+ acute or delayed CNS toxicity
3. Incidence and time to development of radiation necrosis (Kaplan-Meier plot, Cox regression)
 4. Incidence and time to the development of seizures (Kaplan-Meier plot, Cox regression)
 5. Performance status (longitudinal regression)
 6. Overall survival, defined as the interval from registration to death from any cause (Kaplan-Meier plot, Cox regression)
 7. Progression-free survival, defined as the interval from registration to progression or death, whichever occurs first (Kaplan-Meier plot, Cox regression)
 8. Local recurrence, defined as the interval from registration to local recurrence (Kaplan-Meier plot)
 9. Incidence and time to salvage craniotomy (Kaplan-Meier plot, Cox regression)
 10. Incidence and time to additional systemic treatments after reirradiation (Kaplan-Meier plot)

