desirable to obtain a balance between minimizing the total cell number and maximizing the stem-like cell fraction at the end of treatment. This can be achieved, within toxicity and practicality constraints, using an initial phase of hypofractionation to deliver a relatively high dose in a short period to reduce the total cell number with a small number of fractions. By following this with an ultrafractionation phase the slowly proliferating stem-like cell population is enriched at the end of treatment resulting in slower tumor regrowth and, hence, prolonged survival. The proposed treatment schedule consists of 3.96 Gy delivered once per day for the first seven treatment days followed by 1.0 Gy delivered three times per day with a 3.25-hour interval between fractions for the final three treatment days.

Indeed, ultrafractionation has been investigated in glioblastoma with promising results relative to historical controls and no reported grade 3-4 acute adverse events (31), emphasizing the promise and safety of this approach.

We hypothesize that this novel, model-based radiation fractionation scheme will be safe and deliverable for patients with recurrent glioblastoma. This study will use the previously derived mathematical model to optimize a commonly used 2-week dose-fractionation scheme for re-irradiation in glioblastoma (2), currently the standard re-irradiation regimen of the Radiation Therapy Oncology Group (11).

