6. RADIATION THERAPY

6.1 Dose Specifications:

6.1.1 **Treatment Schedule:** Treatment shall consist of a regimen that is biologically equivalent (in terms of biologically effective dose with an alpha/beta ratio of 2) to 35 Gy delivered in 10 fractions over two weeks. Using the regimen developed by Fogh et al (10) and used by RTOG 1205 (35 Gy in 10 fractions) as a standard (11), this protocol has re-optimized the radiation schedule. Radiation therapy will be delivered in 2 phases over 2 weeks with fractions delivered on Monday through Friday only (with no treatments on Saturday or Sunday). All patients will aim to have their first fraction on Monday of week 1. In phase 1, participants will receive 7 daily fractions of 3.96 Gy per fraction. In phase 2, participants will receive 9 fractions of 1.00 Gy per fraction, 3 fractions per day with 3.25 hour interfraction intervals, over 3 days. This idealized treatment schedule is shown in Table 1 and in Figure 1a. Target homogeneity limits and deviations are listed in Table 2. Should any part of the treatment schedule have an anticipated conflict for clinical or logistical reasons (i.e. scheduled department closure for holiday) in which case treatment will not be administered on a given day over the 2-week course, an alternative treatment schedule will be generated utilizing the prediction model for the missing fraction(s). A separate sensitivity analysis was conducted and predicted for a similar benefit of the novel schedule over standard re-irradiation schedule, irrespective of which day of the week treatment is started, as shown in Figure 1b.

Table 1. Idealized Model-Adapted Radiation Schedule*

Week 1	Monday	Tuesday	Wednesday	Thursday	Friday
Dose	1 x 3.96 Gy	1 x 3.96 Gy	1 x 3.96 Gy	1 x 3.96 Gy	1 x 3.96 Gy
Week 2	Monday	Tuesday	Wednesday	Thursday	Friday
Dose	1 x 3.96 Gy	1 x 3.96 Gy	3 x 1.00 Gy (3.25-hour interval)	3 x 1.00 Gy (3.25-hour interval)	3 x 1.00 Gy (3.25-hour interval)

** Schedule subject to predetermined adaptation due to anticipated conflicts (i.e. holidays, department closures, etc....)*

Figure 1a. Idealized Model-Adapted Radiation Schema

[figure not shown]
[figure not shown]

Figure 1b. Sensitivity Analysis for Tumor Response by Day of Treatment Initiation

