12.5 Interim Monitoring Plan

Futility: If two or more patients experience non-adherence events no further patients will be recruited.

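### Does the 1-hour window for three-times-daily fractions need a written reference time to protect the 3.25-hour interval?

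*Combined protocol and SAP*

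**What the plan says.** Section 1.2 describes phase 2 as "1.0 Gy delivered three times per day with a 3.25-hour interval between fractions for the final three treatment days". Section 6.1.1 has "3 fractions per day with 3.25 hour interfraction intervals, over 3 days", and Table 1 repeats the interval for each of the last three days. The readable text gives no clock times; Figure 1a, which also shows the schedule, is not available here.

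Section 12.1 defines a successful patient by "receipt of all scheduled fractions of daily radiotherapy within 24 hours of once daily fractions and within 1 hour of three-times daily fractions". It then explains the tighter window. The model was not sensitive to once-daily timing, but the section adds: "This analysis did reveal the importance of the timing of three-times daily radiation therapy". The criterion that it attaches to those fractions reads "for which feasibility was defined as treatment within 1 hour of the scheduled time".

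This score feeds two decisions. Section 12.1 requires at least 13 successes in 14 patients. Section 12.5 says: "If two or more patients experience non-adherence events no further patients will be recruited". Separately, Section 6.6.3 scores a case as per protocol if it meets the criteria of Section 6.1.1, which include the 3.25-hour interval.

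**The concern.** The treatment is defined by an interval and the endpoint by a clock. If the scheduled time is fixed beforehand, two adjacent fractions may each be on time while the gap between them is far from 3.25 h. Conversely, a day that starts 70 minutes late and keeps both intervals exactly would fail. If the scheduled time is instead counted from the previous fraction, that late day passes and each gap is held within an hour of 3.25 h. One delivery record could therefore be a success on one reading and a non-adherence event on another.

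The rule leaves little slack. One failure in 14 meets the criterion, and two stop recruitment. Because Section 12.5 operates during accrual, a reference time chosen after seeing delivery records could affect the result.

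**Working it through.** **Inputs.** Interval 3.25 h, three fractions a day for three days, so two gaps a day and six per patient (Sections 1.2 and 6.1.1, Table 1). Window 1 h (Section 12.1). Threshold 13 of 14 (Section 12.1). Stop at two events (Section 12.5). Accepted non-adherence limit 30% (Section 12.2).

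**The plan's own figures.** The exact one-sided 95% upper limit for x failures in n is the 0.95 quantile of Beta(x+1, n−x).

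- 5 of 27: Beta(6, 22) gives 35.1% (stated 35%).
- 1 of 14: Beta(2, 13) gives 29.7% (stated 30%).
- 0 of 14: Beta(1, 14) gives 19.3% (stated no higher than 20%).
- 2 of 14: Beta(3, 12) gives 38.5%, above the accepted 30%.

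The stated figures reproduce, and the timing question does not alter them.

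**Gaps that score as success.** Let e be a fraction's deviation in hours from its scheduled time. With fixed times, gap = 3.25 + (e2 − e1) and first-to-third span = 6.5 + (e3 − e1). With times counted from the previous fraction, gap = 3.25 + e. With times counted from the day's first fraction, e1 = 0.

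| Reading | First gap (h) | Second gap (h) | Span (h) |
|---|---|---|---|
| Fixed, early or late (e from −1 to 1) | 1.25 to 5.25 | 1.25 to 5.25 | 4.5 to 8.5 |
| Fixed, late only (e from 0 to 1) | 2.25 to 4.25 | 2.25 to 4.25 | 5.5 to 7.5 |
| From first fraction, early or late | 2.25 to 4.25 | 1.25 to 5.25 | 5.5 to 7.5 |
| From previous fraction, early or late | 2.25 to 4.25 | 2.25 to 4.25 | 4.5 to 8.5 |

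A gap more than 1 h off needs one fraction early and its neighbour late. If only lateness is possible, it cannot occur in a patient who passes.

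**How often a passing patient has a gap more than 1 h off.** This was simulated under the first reading, with assumed normal errors in nine fractions per patient.

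| Within-day correlation | SD 10 min | SD 15 min | SD 20 min |
|---|---|---|---|
| 0 | 0.01% | 2.7% | 16% |
| 0.5 | 0% | 0.04% | 1.4% |
| 0.8 | 0% | 0% | 0.001% |

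**How often exact intervals fail under fixed times.** Suppose each phase 2 day shifts as a whole by a normal amount with both intervals exact. A patient fails if any of three days is more than 60 minutes off. Counting late days only, f = 1 − (1 − Φ(−60/SD))³. Counting early days as well, Φ is doubled. The stopping chance is P(2 or more of 14) under a binomial with probability f.

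| SD (min) | f, late only | Stop, late only | f, early or late | Stop, early or late |
|---|---|---|---|---|
| 20 | 0.4% | 0.1% | 0.8% | 0.6% |
| 25 | 2.4% | 4.5% | 4.8% | 15% |
| 30 | 6.7% | 24% | 13% | 56% |

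For example, at SD 25 min, Φ(−2.4) = 0.0082 and f = 1 − 0.9918³ = 0.0244. The late-only columns match the situation of concern, a day running late. The two scenarios pull in opposite directions and should not be added.

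**The case for a change.** The strongest case for a change is that Section 12.1 itself calls this timing important, and the text says scheduled time rather than interval. The reference point is missing from the endpoint that decides whether an efficacy trial follows. With one failure allowed, a single reclassified patient can settle the result, and the remedy is a few sentences.

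The omission is real: no readable section states the reference time or the direction of the hour. What does not stand is the step from there to a flawed endpoint.

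- The widest gap range needs both fixed times and a window that counts early delivery.
- On-time delivery of booked fractions is a reasonable thing for a feasibility trial to measure, so failing a day more than an hour late may be exactly what is meant.
- An interval rule would need its own tolerance and would still allow a first-to-third span of 4.5 to 8.5 h, as wide as the widest clock reading.
- The sensitivity analysis behind the 1-hour window is not reproduced in the readable text, so nothing here shows that the sponsor's choice departs from it.

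Section 12.1 is also silent on what the 24 hours for once-daily fractions is measured from. That has less weight, since the plan reports no significant model effect of once-daily timing, and Section 6.1.1 provides for anticipated conflicts.

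**Conclusion.** No change is needed. This is a missing detail that a clinic and its analysts would fill in the ordinary way: three appointments booked 3.25 h apart, each fraction compared with its slot. The existing 1-hour rule already needs fraction clock times, so the observed intervals can be derived from the same data. Section 6.6.3 also gives a separate check against the prescribed schedule, although it states no tolerance and is not the endpoint.

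The effect is small unless timing errors are large. With same-day correlation of 0.5 or more and an SD of up to 20 minutes, at most 1.4% of patients would pass with a gap more than an hour off. Late-only whole-day shifts at SD 20 minutes give a 0.1% chance of stopping recruitment. Larger effects need independent errors at SD 15 to 20 minutes, or whole-day shifts at SD 25 to 30 minutes. All of these SDs and correlations are assumptions, because the documents give none. If delivery in this clinic were that irregular, the reference time would matter more. Stating it, with the direction of the hour, would be a courtesy to the reader; replacing the clock score with an interval score is a debatable preference.
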